1.0 INTRODUCTION

1.1 Background and Prior Research

The United States (U.S.) Centers for Disease Control and Prevention (CDC) statistics from August 2011 indicate that male-to-male sexual behavior is associated with the largest number of new HIV infections in the U.S. Men who have sex with men (MSM) represented 61% of newly diagnosed people living with HIV (PLHIV) in 2009, a proportion that has continued to climb in recent years. The recent iPrEx study demonstrated the first biomedical intervention using oral antiretroviral chemoprophylaxis to significantly decrease HIV incidence among MSM¹. While such pre-exposure prophylaxis (PrEP) maybe the most promising new tool to address the domestic MSM epidemic, it may not be appropriate for all MSM in the U.S., as many are not at increased risk for HIV acquisition and such interventions are only cost saving if offered to those at greatest risk². To keep logistics and costs manageable, it is more reasonable to focus on those MSM who are most vulnerable to HIV infection. While analyses for HPTN 061 data have not been completed the incidence data analysis reveals a 2.8 per 100 person-years of follow-up rate overall and 5.9 per 100 person-years of follow-up for young men (less than 30 years). In addition, significant findings suggesting high rates of STIs are correlated with new HIV diagnoses and risk of new HIV infection. As well, incarceration, unemployment and poor education are correlated with new HIV diagnoses. These findings point to the need to understand biological, behavioral and contextual factors that could impede up-take and/or adherence with PrEP.

Among ethnic and racial subgroups of MSM in the U.S., black men who have sex with men (BMSM) are at higher risk. Although BMSM comprise less than 0.4% of the total U.S. population, they accounted for more than 20% of all new infections in 2009. Younger BMSM specifically are at highest risk, experiencing a 48% increase in HIV incidence between 2006 and 2009. Most new HIV infections among BMSM are occurring among men under age 30. Among MSM age 13-24, BMSM accounted for 63% of HIV infections in 2009 while white MSM comprised only 18% of new infections and young Hispanic MSM represented 16% ³.

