2.2 Secondary Objectives

- To describe side effects, toxicities, risk compensation, and STIs among participants who initiate PrEP
- To describe patterns and attributes of PrEP initiation and adherence among participants (e.g., C4, substance use, sociocultural factors and incarceration)
- To measure changes in sexual risk taking behavior among study participants
- To describe reasons BMSM choose to initiate or decline PrEP
- To describe the number of HIV seroconversions, and to analyze viral characteristics (e.g., drug resistance) and the host response to infection in participants who become HIV-infected while on PrEP
- To characterize the participant perception of care and referral plans

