5.3 Enrollment Visit

A participant is considered enrolled at the point in time that he begins enrollment visit procedures (confirmation of locator information during the enrollment visit).

Administrative and Behavioral Evaluations/ Procedures (clinical team)

- Verify locator information
- Behavioral and Psychosocial Risk Survey (ACASI)
- HIV/ STI behavioral risk-reduction counseling
- PrEP discussion
- Offer condoms and other prevention supplies

Note: Indication and Usage for Pre-exposure Prophylaxis will be reviewed with participants as part of a comprehensive package of risk reduction services. In general, sites must refer to the CDC interim guidelines for PrEP administration (http://www.cdc.gov/hiv/prep/pdf/PrEPfactsheet.pdf) and to the guidelines for PrEP Indication (https://www.truvadapreprems.com/#). A manual will be created for all sites to follow when introducing PrEP to participants based on safety and efficacy language found in the ICF under "Study Purpose".

If initiating PrEP:

- Assess participant's initial readiness for PrEP adherence (may be conducted at any time through Week 48)
- o Study product supply
- Autonomy supportive adherence counseling
- PrEP adherence-goal setting
- PrEP Adherence Self-Regulation Questionnaire (participant self-administered)
- C4 including:
 - C4 Case Conference (by staff prior to enrollment)
 - o Care Coordination Measurement Tool (recorded by providers)

Clinical Evaluations/ Procedures

- Interim medical history including concomitant medications
- Symptom-driven physical exam
- Hepatitis B vaccination, if appropriate
- Blood collection
- Urine collection

Laboratory Evaluations/ Procedures

- HIV testing per algorithm in the SSP Manual
- Urine dipstick for protein and glucose (if initial screening result is > trace for either protein or glucose)
- Plasma storage for Pharmacology testing*
- Urine storage for substance use testing

• Plasma storage for QC / Virology testing

*These samples may be tested as controls.

5.4 Weeks 4* and 8

Administrative and Behavioral Evaluations/ Procedures

- Review and update locator information
- Social Harms and AE Assessment
- HIV/STI behavioral counseling (pre- and post-test), including risk-reduction counseling
- PrEP discussion
- Offer condoms and other prevention supplies

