5.10.2 Focus Groups with Site Staff

Each of the three sites for HPTN 073 will conduct one focus group with the C4 team at the end of the study to elicit feedback on what resources they believe were necessary to optimally implement a C4-based PrEP program. This will include (1) resources that were available onsite (2) resources that were available in the community, (3) resources that were not available during the course of the study, and (4) discussion of how resources would have improved their ability to provide care. The C4 team will be consented for the focus group immediately prior to the conduct of the focus group and after all

participants have completed the study. A staff member will review the consent, or read it aloud with the entire group and then will answer any questions. During the consent procedure, staff will go over pertinent aspects of the focus group activity with participants, including ground rules, the structure of group discussion, potential risks, benefits, and compensation. The data from CCMT and focus groups will be triangulated to form a profile of the human and space resource needs across the three study sites.

5.11 Participants who have Suspected or Confirmed HIV at Screening or During the Study

In the case of suspected HIV infection at the Screening visit, HIV status will be confirmed using local HIV testing guidelines. Participants who have a reactive or positive HIV test at Screening are not eligible for enrollment, even if subsequent testing indicates that they are not HIV infected.

Participants who have a reactive HIV test result at a follow-up visit will be instructed to discontinue their study medication immediately and will be further evaluated following procedures in the SSP Manual.

In addition, if a participant has signs or symptoms consistent with acute HIV infection, or expresses a concern about recent HIV acquisition, testing will be performed using an HIV RNA test if antibodybased HIV tests are non-reactive. Regardless of whether HIV RNA testing is used for diagnostic testing, HIV infection that is diagnosed after the Screening visit must be confirmed in all cases using samples collected on two different days.

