7.3.2 Secondary Analyses

Analyses for secondary objectives will be mostly descriptive. Line listings as well as summary descriptive statistics including means, medians, and proportions with 95% exact or asymptotic confidence intervals as appropriate at each visit, will be used for the following secondary objectives. Specifically,

- Use GEE or random effects models to describe longitudinal patterns and their correlates of PrEP initiation and adherence among participants (e.g.: C4, substance use, sociodemographics, sociocultural factors, risk practices and incarceration)
- To describe side effects and toxicities of PrEP among participants in the PrEP demonstration project. AEs will be tabulated, overall and by grade. For any reasonably common AEs (> 20 events), exploratory analyses will be conducted to assess correlates of the AE, including demographics and duration and patterns of PrEP use, within the limits imposed by the small expected number of events.
- Describe and produce summary plots for longitudinal changes in sexual risk-taking behavior among study participants
- List and summarize reasons BMSM choose to initiate or decline PrEP
- List and summarize HIV seroconversions and characteristics of the infection(s) (e.g., viral set point, drug resistance patterns) in participants who initiated PrEP
- Use Kappa-statistics to assess agreement of adherence under different measures.

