12.0 APPENDIX IB - ADDITIONAL PROCEDURES FOR PARTICIPANTS WITH CONFIRMED HIV INFECTION

	Time of diagnosis (confirmatory visit)	Weeks 4, 8, 13, 26, 39, and 52 (if after HIV diagnosis)	Every 12 weeks after Week 52 ¹
Behavioral Risk Assessment (ACASI)	Х	x ²	х
CD4 cell count testing	Х	Х	Х
HIV viral load testing	Х	Х	Х
HIV genotyping ³	Х		
Additional plasma storage for HPTN NL testing ^{4,5}	Х	Х	Х
Lysed PBMCs for Pharmacology testing ⁶	Х		

¹ Participants with confirmed HIV infection will continue in the study, off of study drug. Any participants who acquire HIV infection during the study will permanently discontinue study product and will be followed after Enrollment at regular visits until the last HIV-uninfected participant reaches Week 52 at that site.

² Excluding Weeks 4 and 8

³ HIV genotyping will be performed in real-time at a laboratory that is used for clinical care at the study site; these results will be provided to the study site and participant. Additional resistance assessments/testing may be performed retrospectively using stored samples shipped to the HPTN NL; those results will not be reported back to study sites or participants.

⁴ In addition to plasma stored at other scheduled visits, additional plasma aliquots must be stored at the time of HIV diagnosis (confirmatory visit) and other visits indicated in Appendix IB. Stored plasma samples from HIV seroconverters will be shipped to the HPTN NL; sites should store samples until they receive a request for shipping from the SDMC. These samples may be used for HIV diagnostic testing, QA testing, Pharmacology testing, resistance testing, and other testing (see footnote 5).

⁵ Additional testing may be performed at the HPTN NL. At the discretion of the HPTN NL, this testing may be performed at another laboratory (e.g., at one of the study sites, at the U.S., CDC, or at another laboratory with special expertise). Results of this testing will not be returned to study sites or study participants. This testing may include additional HIV genotyping/sequencing assays, HIV phenotyping, HIV subtyping, minority variants assays, other assays to characterize HIV viruses and/or the host response to HIV infection.

⁶ If the time of HIV diagnosis (confirmatory visit) occurs at a visit where lysed PBMCs are not already being collected, they should also be collected at this visit for any participant who reports that he used PrEP within 60 days of the confirmatory visit.

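### Objective, endpoint and analysis name three different populations for HIV seroconversions, and the analysis as worded leaves out men who never started PrEP

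*Protocol*

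**What the plan says.** Three places in the protocol fix who belongs to this endpoint.

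- **Objective (Section 2.2).** The first clause is "To describe the number of HIV seroconversions", with no population attached. The second clause concerns viral characteristics and "the host response to infection in participants who become HIV-infected while on PrEP".
- **Endpoint (Section 7.1).** Incident seroconversions and their characteristics are a secondary endpoint, again without restriction, and HIV testing is planned at all study visits. Section 5.11 adds that anyone with infection confirmed after Enrollment stays in follow-up, whether or not he took PrEP.
- **Analysis (Section 7.3.2).** The only bullet on this endpoint reads "List and summarize HIV seroconversions and characteristics of the infection(s) (e.g., viral set point, drug resistance patterns) in participants who initiated PrEP".

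Section 7.3.1 allows initiation to mean use at any point in the study. No other analysis bullet mentions infections in men who never started.

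**The concern.** The limit in the analysis matches neither the endpoint nor either clause of the objective. It is narrower than the unrestricted count and wider than the on-PrEP group, because men infected after stopping are also initiators.

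An analyst who follows Section 7.3.2 to the letter would report a seroconversion count that leaves out men who declined PrEP. A reader could take that count for the study total. In a study that offers PrEP and lets men decline, infections among those who declined are part of what the objective asks for, and the study tests and follows these men in order to see them.

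**Working it through.** **1. The two ways to read the analysis bullet.**

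- *Natural reading.* The closing limit governs both items joined before it, the seroconversions and the characteristics. The count is then restricted to starters, against the first clause of the objective and the endpoint.
- *Alternative reading.* The limit governs only the characteristics. The count is then unrestricted, as in the objective. The virology group is still ever-initiated in Section 7.3.2 but on-PrEP in Section 2.2, and the two differ by the men infected after stopping.

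The passages need reconciling under either reading.

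**2. The restriction depends partly on the outcome.** Appendix IA, Note 1 requires a man who wishes to start after Enrollment to meet all Screening criteria again. Section 3.2 excludes anyone with a reactive HIV test. A man whose infection is detected before he starts can therefore never become an initiator, and his infection always falls outside the summary.

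**3. Size. Inputs from the protocol:**

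- N = 225 (Schema; Section 7.2).
- Acceptance a = 33%, 50% or 67% (Section 7.2).
- Background incidence r: "2.8 per 100 person-years of follow-up rate overall", from an earlier study in this population (Section 1.1).
- Loss to follow-up of 10% to 20% (Section 7.2).

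The protocol gives no expected number of seroconversions to reproduce. The acceptance scenarios come with their own intervals, which do reproduce. The normal approximation p ± 1.96 × √(p(1 − p)/225) gives 26.9% to 39.1% at 33% and 60.9% to 73.1% at 67%, matching the stated 27% to 39% and 61% to 73%. At 50%, the whole number 113/225 gives 43.7% to 56.8%, matching the stated 44% to 57%.

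**Assumptions not in the protocol:**

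- Follow-up T = 0.9 person-years per man, that is 20% lost with half a year lost each: 1 − 0.20 × 0.5.
- Never-starters have the same background risk as starters.
- Starters are counted as starting at Enrollment.

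Expected omitted infections = 225 × (1 − a) × T × r:

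- a = 67%: 225 × 0.33 × 0.9 × 0.028 = 1.9
- a = 50%: 225 × 0.50 × 0.9 × 0.028 = 2.8
- a = 33%: 225 × 0.67 × 0.9 × 0.028 = 3.8

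With no loss (T = 1) the figures are 2.1, 3.2 and 4.2.

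**4. Share of all infections.** Let e be the reduction in incidence among starters (assumed, 0 to 90%) and RR the background risk of never-starters relative to starters (assumed).

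Share in never-starters = (1 − a)RR / [(1 − a)RR + a(1 − e)].

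- RR = 1: from 0.33/(0.33 + 0.67) = 33% (a = 67%, e = 0) to 0.67/(0.67 + 0.033) = 95% (a = 33%, e = 90%).
- RR = 0.5: 20% to 91% over the same scenarios.
- RR = 2: 50% to 98%.
- Acceptance of 90%, above the planned range, with RR = 1: 10% to 53%.

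**The case against.** The best defence is the alternative reading: the bullet mirrors the objective, first a count and then virology in exposed men, and limiting virology to men with PrEP exposure suits the purpose in Section 5.11 of learning about HIV outcomes after such exposure. This reading is possible, so the omission of never-starters follows from the more natural reading and is not certain. It does not remove the conflict between ever-initiated and on-PrEP. It is also fair that line listings are planned, so each listed man's PrEP status could be shown individually. That does not help men who are not listed.

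The size depends on assumptions. Section 7.2 uses the acceptance rates to illustrate interval width and does not forecast them, and the share moves widely with e, RR and acceptance.

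Four stronger readings might be inferred, and the protocol does not support them:

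- *The lack of person-time is an error.* The objective asks for a number and the secondary analyses are mostly descriptive. Rates with intervals are commonly left to a statistical analysis plan. Section 1.1 gives the incidence figures as background, and no comparison with them is planned.
- *Men already infected at Enrollment will be counted.* Section 5.3 does say "A participant is considered enrolled at the point in time that he begins enrollment visit procedures". But the endpoint is incident infection, HIV is tested and plasma stored at that visit, and Section 9.3.1 has a confirmation rule for a reactive Enrollment test. Nothing says that such an infection counts as incident.
- *Exposure at infection will be misjudged because PBMCs may be taken after drug is stopped.* Nothing makes the confirmatory-visit sample the measure of exposure. Appendix IB, footnote 4 already allows pharmacology testing of seroconverters' stored plasma. Any figure for drug decay would need a half-life and a confirmation delay that the protocol does not give.
- *Up to 8 infections would be lost.* That applies the rate of 5.9 per 100 person-years, which Section 1.1 gives for men under 30, to every never-starter.

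**Conclusion.** The concern holds as an inconsistency of population. Sections 2.2, 7.1 and 7.3.2 describe all enrolled men, men infected while on PrEP, and men who ever started, and they cannot all govern the same summary. On its natural reading Section 7.3.2 drops every infection in a man who never started, including any detected before he could start.

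At 2.8 per 100 person-years this is about 2 to 4 infections, given 33% to 67% acceptance, 0.9 person-years per man and equal background risk. Under the protocol's acceptance scenarios that could be a large share of the total, but the total is small and the share rests on assumed efficacy and relative risk. Section 1.2.5 itself expects incident infections to be uncommon, so losing even a few would alter the picture for this secondary endpoint. No primary endpoint is touched.

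**What to change.** Reword the bullet in Section 7.3.2 so that incident HIV seroconversions are listed and counted among all enrolled participants, classified by PrEP status at the estimated time of infection: never started, on PrEP, or started and stopped. State which of these groups the viral-characteristics and host-response analysis covers, and make that agree with the second clause of the objective in Section 2.2.

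Person-years with exact Poisson intervals by exposure state would be a useful optional addition.

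The cost is a change of wording and a little extra descriptive tabulation. HIV test results and PrEP use are already recorded for all participants, so no new visits or samples are needed.

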7.3.3 Qualitative Data Analyses

Qualitative data analyses will be conducted on an ongoing basis in collaboration with data collection. Thematic coding will be used to analyze the data from the individual interviews based on a grounded theory approach. The Consensual Qualitative Research Method (CQR) will be used by the study team to analyze the data. The CQR method provides a reliable, systematic, and rigorous method in conducting qualitative data analyses - recognizing the importance of context, incorporating an inductive analytic process, using a team and making decisions by consensus, using auditors, and verifying results by systematically checking against the raw data. The key elements of conducting qualitative data analyses using the CQR method include: (1) develop and code domains, (2) construct core ideas, and (3) develop categories to describe consistencies across cases (cross analysis).

8.0 HUMAN SUBJECTS CONSIDERATIONS

This protocol and the template informed consent form(s) contained in Appendix II and any subsequent modifications will be reviewed and approved by the HPTN SRC and DAIDS Prevention Science Review Committee (PSRC) with respect to scientific content and compliance with applicable research and human subjects' regulations.

The protocol, site-specific informed consent form, participant education and recruitment materials, and other requested documents and any subsequent modifications will also be reviewed and approved by the ethical review bodies responsible for oversight of research conducted at the study site.

Subsequent to initial review and approval, the responsible IRBs will review the protocol at least annually. The Investigator will make safety and progress reports to the IRBs at least annually and within three months of study termination or completion. These reports may include the total number

of participants enrolled in the study, the number of participants who completed the study, all changes in the research activity, and all unanticipated problems involving risks to human subjects or others. Study sites are responsible for the submission of continuing reviews to the DAIDS Protocol Registration Office, in accordance with the current DAIDS Protocol Registration Policy and Procedure Manual.

8.1 Informed Consent

Written informed consent will be obtained from each study participant. Each study site is responsible for developing study informed consent forms for local use, based on the template in Appendix II that describes the purpose of the study, the procedures to be followed, and the risks and benefits of participation, in accordance with all applicable regulations. If applicable, the study site also is responsible for translating the template form into local languages and verifying the accuracy of the translation by performing an independent back-translation.

Literate participants will document their provision of informed consent by signing their informed consent forms. Any other local IRB requirements for obtaining informed consent from non-literate persons will also be followed.

Participants will be informed that they can decline to participate without any change in their relationship with their local Department of Public Health or STD clinic. They will also be informed that they can quit the study at any time.

8.2 Incentives

Pending IRB approval, participants will be compensated for their time and effort in this study, and/or be reimbursed for travel to study visits and time away from work. Site-specific reimbursement amounts will be specified in the study informed consent forms.

8.3 Confidentiality

All study-related information will be stored securely at the study site and/ or collaborative partner. All participant information will be stored in locked file cabinets in areas with access limited to study staff. All laboratory specimens, reports, and study data-collection, process and administrative forms will be identified by a coded number to maintain participant confidentiality. All records that contain names or other personal identifiers, such as locator forms and informed consent forms, will be stored with restricted access according to local SOPs. All local databases will be secured with password-protected access systems.

Participant study information will not be released without the written permission of the participant, except as necessary for monitoring by the NIAID and/or its contractors, Gilead Sciences, Inc., representatives of the HPTN CORE, SDMC, and/or NL, OHRP, other government and regulatory authorities, and/or site IRBs.

The HPTN will obtain a Certificate of Confidentiality from the U.S. Department of Health and Human Services that will be applicable for this study. Sites may register under the Certificate through the HPTN CORE once they have obtained local IRB approvals for the study. This Certificate protects study staff from being compelled to disclose study-related information by any Federal, State or local civil, criminal, administrative, legislative or other body.

